7.4.3 Day 1 (First Day after Surgery, Hospitalization)

The following procedures and assessments will be conducted at this visit:

Collect CSF sample/ LP

LP vital signs will be collected and recorded by the study team before and after the LP only if the LP is performed on an outpatient basis.

Concomitant medications will be administered according to standard of care

Collect blood sample

Laboratory assessments

Study drug or placebo administration (every 6 hours until 3 days after surgery or hospital discharge, whichever comes first, up to 13 doses maximum) by the patient's clinical care team

Grade II or higher AEs recorded

Delirium Screening will be administered with 3D-CAM or CAM-ICU

7.4.4 Days 2-4 (Hospitalization)

The following procedures and assessments will be conducted at this visit:

Concomitant medications will be administered according to standard of care

Study drug or placebo administration (every 6 hours until the 3rd day after surgery or hospital discharge, whichever comes first, for a maximum of 13 doses) given by the patient's clinical care team.

Grade II or higher AEs recorded

Delirium Screening will be administered with 3D-CAM or CAM-ICU until postoperative day 5 or hospital discharge (whichever occurs first).

7.4.5 6 weeks (+/- 3 weeks) Follow-Up

The following procedures and assessments will be conducted at this visit:

Neurocognitive testing will be done either in-person or remotely via teleconference (may include HVLT-R; BVMT-R; WAIS-III—Digit Span, Digit Symbol Coding subtests, TMT Parts A & B, COWAT, MoCA, and Grooved Pegboard; STOPBang (only if it wasn't performed at the preoperative visit) VAS pain assessment, Falls assessments, Timed Up and Go Test, Romberg Test)

Laboratory assessments

DASI

Psychological measures (including CES-D, STAI, Hopkins SCL-90)

SF-36

Collect CSF samples / LP

Vital signs will be collected and recorded by the study team before and after the LP, only

if the patient is not already hospitalized as an inpatient at this time.

Collect blood samples

Grade II or higher AEs recorded

Delirium assessment (using either the 3D-CAM instrument, or the CAM-ICU instrument in the unlikely case that the patient is intubated at the time of this study visit).

STOP-Bang sleep apnea screening assessment may be performed, if it was not already completed at the baseline study visit or at another point during the study.

7.4.6 Schedule of Events

Table 2: Schedule of Study Events for Trial

	Screening/ Baseline Study Visit	Within 1 week before surgery	Day 0 Surgery	Day 1 ^a Hospitalization	Days 2-4 Hospitalization	6 weeks (+/- 21 days) Follow- up
Informed consent	X					
Enrollment	X					
Randomization		X				
Demographics (age, sex, and race)	X					
Vital signs			X b, e	X b		X b
Medical history	X					
Neurocognitive testing ^c	X					X
Continuous Heart Rate Recording			X			
Laboratory assessments (additional routine clinical pre- + post-op labs will also be recorded)			X	X		X
Duke Activity Status Index	X					X
Psychological/physical measures ^d	X					X
Short Form-36	X					X
Lumbar puncture, Collect CSF samples			X ^e	X		X
Concomitant medications	X		X	X	X	X
Collect blood sample			X ^f	X		X
Drug administration ^g			X	X	X	
Electroencephalogram (EEG)			X ^h			
Grade II or higher AEs/ all serious AEs			X	X	X	X
3D-CAM or CAM-ICU for delirium screening	X		X	X	X ⁱ	X
Biomarker assays			X	X		X
Genotyping assays			X ^f			
Inflammatory protein analysis			X	X		X
CSF protein analysis			X	X		X

AE, adverse event; CSF, cerebrospinal fluid;
QOL, quality of life

^a 24 (+/- 2) hours post-surgery.

^b LP vital signs will be collected and recorded by the study team before and after the LP only if it is performed on an outpatient basis.

^c May include Hopkins Verbal Learning Test-Revised; BVMT-R ; Wechsler Adult Intelligence Scale-III—Digit Span, Digit Symbol subtests; Wechsler Test of Adult Reading; Trail Making Test Parts A & B; Grooved Pegboard; Montreal Cognitive Assessment (MoCA); STOPBang Questionnaire; visual analog scale pain assessment;

^d May include Center for Epidemiological Studies-Depression, State Trait Anxiety Inventory, Hopkins Symptom Checklist, Falls assessments, Timed Up and Go, and Romberg Assessments.

^e Between the time of consent and the scheduled anesthesia/surgery start time on the day of surgery.

^f Between the time of consent and the scheduled anesthesia/surgery start time on the day of surgery.

^g w/in 1 hr before the scheduled or actual start time of surgery and continuing every 6 hours through postoperative day 3 (up to 13 doses maximum) or hospital discharge, whichever occurs first

^h Immediately before , during, and after surgery/anesthesia. In the event that sufficient personnel or equipment are unavailable, or in the event that two MARBLE patients are having surgery at the same time, or in the event that there is insufficient time to place the EEG sensor on that patient's head before the start of surgery, the study team may not record EEG from all patients or at all points before, during, and just after surgery/anesthesia. Auditory tones will be played, and auditory event-related potentials will be recorded if the pre-op and surgical workflow allows and if study personnel are available.

ⁱ This will be administered until postoperative day 5 or hospital discharge (whichever occurs first).

8 ASSESSMENT OF SAFETY

8.1 Specification of Safety Parameters

8.1.1 *Definition of Adverse Events (AEs)*

An AE is any untoward medical occurrence associated with the use of a drug in a participant, whether or not considered drug related. An AE can, therefore, be any unfavorable and unintended sign, including an abnormal laboratory finding, for example, symptom, or disease temporally associated with the use of a pharmaceutical product. Diseases, signs, symptoms, or laboratory abnormalities already existing at randomization are not considered AEs unless they worsen (i.e., increase in intensity or frequency). Surgical procedures planned before randomization and the conditions leading to the need for these surgical procedures are not AEs.

8.1.2 *Definition of Serious Adverse Events*

An AE is considered serious if any of the following occur or the investigator believes any of the following outcomes may occur:

1. Death.
2. Life-threatening AE: places the participant, in the view of the investigator, at immediate risk of death at the time of the event as it occurred. It does not include an AE that, had it occurred in a more severe form, might have caused death.
3. Persistent or significant disability or incapacity or substantial disruption of the ability to conduct normal life functions.
4. Congenital abnormality or birth defect.
5. Requires inpatient hospitalization or prolongation of existing hospitalization with the following exceptions:
 - Preplanned (before the trial) hospital admissions, unless the hospitalization is prolonged
 - Planned admissions (as part of a trial, e.g. routine biopsies)
 - Re-hospitalizations (which occur less than 24 hours after discharge from index hospitalization)
 - Elective procedures
 - Emergency room visits
6. Important medical events that may not result in death, be life threatening, or require inpatient hospitalization may be considered a serious AE (SAE) when, based on appropriate medical judgment, they may jeopardize the participant and may require medical or surgical intervention to prevent one of the serious outcomes listed above. This determination is based on the opinion of the investigator.
7. SAEs that are thought to be related (i.e. more likely than not to be related) to the study drug will be reported to the FDA and all other appropriate regulatory bodies within 15 days of the study time documenting the SAE. SAEs thought not to be related to the study drug will be reported on a yearly basis.

8.1.3 *Definition of Unanticipated Problems*

Unanticipated problems involving risks to participants or others include, in general, any incident, experience, or outcome that meets all of the following criteria:

Unexpected in terms of nature, severity, or frequency given (a) the research procedures that are described in the protocol-related documents, such as the IRB-approved research protocol and informed consent document; and (b) the characteristics of the participant population being studied

Related or possibly related to participation in the research (“possibly related” means there is a reasonable possibility that the incident, experience, or outcome may have been caused by the procedures involved in the research)

Suggests that the research places participants or others at a greater risk of harm (including physical, psychological, economic, or social harm) than was previously known or recognized

8.2 Classification of an Adverse Event

8.2.1 Severity of Event

Assessment of severity of an event will be based on the following:

Mild: Is generally transient, does not interfere with usual activities, and is easily tolerated by the participant.

Moderate: Causes sufficient discomfort and interferes with usual activities.

Severe: Causes considerable interference with usual activities and may be incapacitating.

Whenever appropriate and/or possible, we will define AE's by the NIH Common Terminology Criteria for Adverse Events (available online at

https://ctep.cancer.gov/protocoldevelopment/electronic_applications/docs/CTCAE_v5_Quick_Reference_5x7.pdf

Multiple grade I (i.e. mild) AEs per CTCAE criterion typically occur after major non-cardiac surgery in older adults (i.e. our study population). Examples of such grade I AEs that occur in virtually every older adult after major non-cardiac surgery include hemoglobin declines to between 10 mg/dL and the lower limit of the normal range, serum Ca++ drops to between 8.0 and the lower limit of the normal range, WBC count increases to the 10-20 range, etc. Thus, to avoid capturing a massive amount of such grade I AEs that are unlikely to be related to study drug administration, here we will capture and report just those AEs of grade II or higher, and all SAEs.

8.2.2 Relationship of Study Agent

Assessment of the relationship of an event to the study agent will be based on the following:

Unrelated = None; Remote

- None (unrelated, not related, no relation)
 - Unreasonable temporal relationship between administration of the study agent and the onset of the AE (e.g., the event occurred either before, or too long after, administration of the study agent for it to be considered drug related)
 - Causal relationship between the study agent and the AE is biologically implausible (e.g., death as a passenger in an automobile accident)
 - Clearly more likely alternative explanation for the AE is present (e.g., typical adverse reaction to a concomitant drug and/or typical disease-

related event)

- Remote (unlikely, doubtful, improbable)
Little evidence to suggest there is a causal relationship and there is another reasonable explanation for the event.

Related = Possible, Probable

- Possible
 - There is some evidence to suggest a causal relationship (e.g., the event occurred within a reasonable time frame after administration of the study agent); however, the influence of other factors may have contributed to the event (e.g., the participant's clinical condition, other concomitant medications, or concurrent illness)
- Probable
 - There is evidence to suggest a causal relationship between the event and the study agent, and the influence of other factors is unlikely.

The investigator should consider the following when assessing causality:

- Temporal associations between the study agent and the event
- Pre-existing risk factors or concurrent illness
- Plausible mechanism

8.2.3 *Expectedness*

The investigator will be responsible for determining whether a grade II or higher AE is expected or unexpected. A grade II or higher AE will be considered unexpected if the nature, severity, or frequency of the event is not consistent with the risk information previously described for the study agent in the protocol.

8.3 Time Period and Frequency for Event Assessment and Follow-up

The investigator will record all reportable events starting from the time just after the first administration of study drug (or placebo) until the last trial-related procedure/visit. At each trial visit, the investigator or study team will inquire about the occurrence of grade II or higher AE and any SAEs since the last visit. Events will be followed for outcome information until resolution or stabilization. Adverse events of grade II or higher for participants who discontinue trial participation will be collected/reported through at least the time of discontinuation.

When additional relevant information (final diagnosis, outcome, results of specific investigations, etc.) becomes available, the investigator will submit this additional information to the DSMB at the time of the next DSMB report (or earlier, if deemed appropriate by the PI).

8.4 Reporting Procedures

All grade II or higher AEs that occur between the time immediately following the first administration of study drug (or placebo) until the last trial-related procedure/visit will be recorded. Adverse events may be volunteered by subjects and/or solicited at each assessment by the investigator or designee.

Recording will be performed in a concise manner using standard, acceptable medical terms. The research team (and the Principal Investigator) will make every effort to establish a diagnosis of the event based on the presenting signs, symptoms, and/or clinical information. In such cases, the diagnosis will be documented as an AE/SAE.

Diseases, signs, symptoms, or laboratory abnormalities already existing at enrollment will not be considered AEs unless they worsen (i.e., increase in intensity or frequency). Surgical procedures planned before enrollment and the conditions leading to these measures are not AEs, and the normal post-operative recovery course of a surgical procedure planned before enrollment also will not constitute an AE. Thus, for example, if a study patient has a planned knee replacement surgery before he or she enrolls in the study, the patient has this surgery, and a postoperative knee x-ray shows the normal postoperative presence of the replacement knee, this will not be considered an AE.

If, in the investigator's judgment, a clinically significant worsening from baseline is observed in any laboratory or other test parameter (e.g., ECG), physical examination finding, or vital sign, a corresponding clinical AE should be recorded. If the cause is not known, the abnormal test or finding should be recorded as an AE, using appropriate medical terminology (e.g., thrombocytopenia, peripheral edema, QT prolongation). If this AE is of grade II or higher per CTCAE criteria, this event will be recorded and reported to the DSMB+.

8.4.1 *Serious Adverse Event Reporting*

8.4.1.1 *Reporting to the DSMB and IRB*

All drug-related SAEs (i.e. if thought to be drug-related, or more likely than not to be related to the drug), occurring between the time immediately following the first administration of study drug (or placebo) until the last trial-related procedure/visit will be reported by the investigator or qualified designee within 5 working days of first becoming aware of the event to the IRB and DSMB. For SAEs deemed "probably" drug-related, reporting to the IRB and/or FDA will occur within appropriate time windows, per institutional and FDA requirements.

8.4.1.2 *Reporting to Regulatory Authorities*

All SAEs will be reviewed for expectedness by the Principal Investigator or another investigator designated by the Principal Investigator. SAEs determined to be "probably" related to the investigational drug and that are unexpected according to the protocol will be reported in an expedited manner to the FDA, in accordance with 21 CFR 312.32. For unexpected drug-related SAEs that result in death or are considered life threatening, they will be reported to the FDA as soon as possible but in no case later than 7 calendar days after the sponsor's initial receipt of the information. For all other unexpected, drug-related SAEs, reporting to the FDA will occur no later than 15 days after the event. Non drug-related SAEs will be reported to the FDA on a yearly basis.

8.5 *Trial Halting Rules*

At the end of each 67 patient dose cohort, grade II or higher AEs (and all SAEs) will be provided to and reviewed by the DSMB, which will then consider whether the study can continue or whether it needs to be stopped and/or other corrective action needs to take place. Due to a clerical error by the Investigational Drug Services that prepares our drug/placebo doses, 69 patients were randomized to the first patient cohort rather than 67. Additionally, because enrollment happens at consent, and not all patients that consent will be randomized, we will keep enrolling patients until we reach 67 consented and randomized patients in each of the last two cohorts.

8.6 Safety Oversight

A DSMB composed of clinical/translational neuroscience investigators from outside of Duke (i.e. a DSMB+) will be convened before trial initiation and will evaluate the incidence of AEs in the placebo vs CN-105 treatment groups at the completion of each 67 patient cohort, as enrollment for the next 67 patient study cohort (and the next successive higher dose of CN-105) is beginning.

The DSMB+ will be empowered to halt the study during enrollment of the next 67 patient cohort if the following two conditions are met during the DSMB+ review of the prior 67 patient study cohort. First, that there is an apparent, consistent and persistent evidence of net harm (i.e. grade II or higher AE's, or SAEs, that occur at significantly increased frequency in patients who receive CN-105 vs placebo and which are viewed as likely resulting from CN-105 treatment rather than other factors or chance), and second that this net harm is perceived to overwhelm any benefit from study drug treatment and the overall knowledge to be obtained from the study. In this way, participants can be prevented from receiving higher doses of CN-105 if we determine that lower doses are consistently associated with an increased incidence of grade II or higher AEs.

9 CLINICAL MONITORING

Clinical site monitoring will be conducted by the on-site study team to ensure that the rights and well-being of human subjects are protected, that the reported trial data are accurate, complete, and verifiable, and that the conduct of the trial is in compliance with the currently approved protocol/amendments, with GCP, and with applicable regulatory requirements. The study team will perform this monitoring at least on a quarterly basis.

10 STATISTICAL CONSIDERATIONS

10.1 Description of Statistical Methods and Analysis Plans

10.1.1 General Approach

Data will be analyzed using standard analysis programs, including SAS and SPSS. R may also be used if necessary.

10.1.2 Safety and Feasibility Endpoints

Safety Analysis: Our DSMB will examine all grade II or higher AEs and all SAEs in CN-105 and placebo treated patients. The expected rate of moderate and severe adverse events in this patient population is 5% each, based on historical Duke orthopedic surgery data; thus we expect similar AE rates in this trial in placebo- treated patients. At the end of each 67 patient randomized group, the DSMB will examine grade II or higher AE rates in drug-treated vs placebo-treated patients, and consider whether the study should be stopped or whether other corrective action should take place. An independent statistician will prepare summary reports (including all grade II or higher AE rates in drug vs placebo treated patients) for review by the DSMB+ at the end of each 67 patient randomized group. Thus, the study team (and the primary study statistician) will thus remain blinded to patient treatment assignment throughout the course of the study. Due to a clerical error by the Investigational Drug Services that prepares our drug/placebo doses, 69 patients were randomized to the first patient cohort rather than 67. Additionally, because enrollment happens at consent, and not all patients that consent will be randomized, we will keep enrolling patients until we reach 67 consented and randomized patients in each of the last two cohorts.

Assuming that we continue with all three dose groups, at study completion we will have ≥ 117 total CN-105 treated patients and ≥ 39 placebo-treated patients. Given the aforementioned expected grade II or higher AE rates in placebo-treated patients, at completion we will have $>80\%$ power (with $\alpha=0.05$) in a two- sample two-sided unpooled variance chi-square test to detect an absolute difference of 14.8% between grade II or higher AE rates seen in placebo vs CN-105 treated patients. We will also track the rates of other grade II or higher AEs recorded by the patient’s surgical team in the medical record; at study completion we will use 2 sided t tests to compare the rates of any other grade II or higher AEs between placebo vs CN-105 treated patients.

Feasibility Analysis: We will report the observed rate of doses administered within the required time window and the 95% confidence interval. Each dose will be counted as an independent observation. The total number of doses correctly administered (i.e. within 90 min of the scheduled administration time) divided by the number of prescribed doses will define our dosing feasibility rate. Post-hoc feasibility analysis will be performed among all patients, as well as specifically in patients receiving the study drug only, and by dose level to determine if the drug itself or drug dose level affects feasibility.

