4 TRIAL DESIGN AND ENDPOINTS

4.1 Description of Trial Design

Trial initiation will start with the enrollment of the first participant, which will occur only after the external institutional review board (IRB) as well as the Duke University Medical Center IRB has approved the protocol.

Participants age 60 and over who are scheduled to undergo non-cardiac, non-neurologic surgical procedures that will take more than 2 hours and who are scheduled to be admitted to the hospital after surgery at Duke University Medical Center (DUMC) or one of its affiliate hospitals (Duke Regional Hospital, Duke Raleigh Hospital) will be prospectively enrolled in this trial.

Trial participants will undergo cognitive testing and complete QOL assessments within 2 months before surgery and again 6 weeks +/- 3 weeks after surgery. These participants will receive either CN-105 or placebo, within one hour before the scheduled or actual start time of surgery and continuing every 6 hours through postoperative day 3 (up to 13 doses maximum) or hospital discharge, whichever occurs first. Each case start time will be defined by the study team as either the start of the surgery/procedure or the start of anesthesia.

We planned to enroll up to 250 patients in this phase 2 escalating dose study, with escalating CN-105 doses occurring in three successive groups of 67 randomized patients each. Due to a clerical error by the Investigational Drug Services that prepares our drug/placebo doses, 69 patients were randomized to the first patient cohort rather than 67. [Additionally, because enrollment happens at consent, and not all patients that consent will be randomized, we will keep enrolling patients until we reach 67 consented and randomized patients in each of the last two cohorts.](#)

In each group of 67 patients, 50 will receive a given dose of CN-105 and 17 will receive placebo. In our recent MADCO-PC study(Duke IRB protocol #45180), ~80% of patients returned for the 6 week assessment. Thus, enrolling 67 patients in each group ensures ≥ 52 patients (i.e. 39 CN-105-treated; 13 placebo treated) will complete the 6 week +/- 3 weeks postop assessment.

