4.2 Trial Endpoints

4.2.1 Primary Endpoint

The primary endpoint is to determine whether there is a significant difference in grade II or higher adverse events (AEs) between participants in each dose cohort of CN-105 vs. those who receive placebo.

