5.4.2 Handling of Participant Withdrawals or Terminations

A recent phase I trial did not identify any specific adverse events or safety concerns with CN-105 (Guptill J et al, 2017). Nonetheless, if at any time during the dosing period, participant safety is considered at risk due to study agent-related adverse events per the judgement of the external Data Safety Monitoring Board (or DSMB+) and the PI, then the study agent will be immediately discontinued. Although the DSMB+ is only scheduled to convene and review reports (including grade II or higher AE, and SAE information) at the completion of each 67 patient cohort, the PI may also request that the independent statistician prepare additional interim analyses and provide these to the DSMB+ at any time. For example, this may be useful and/or appropriate if there is a severe SAE (such as a patient death) and the PI wishes to have the DSMB+ review grade II or higher AE rates and data up to an including this severe SAE, and make interim recommendations to the study team.

Since CN-105 modulates the inflammatory response, it could theoretically impair the response to infection. Thus, in an abundance of caution, the study agent will be discontinued in any patient who develops any intracerebral or systemic infection.

If a participant has clinically significant laboratory and/or electrocardiographic abnormalities that are considered to be related to the study agent in the judgement of the Principal Investigator or the DSMB, study agent treatment discontinuation will be evaluated.

Primary study analyses will be conducted using intention to treat analysis (i.e. with patients included in the groups to which they were randomized even if they did not correctly receive all doses to which they were randomized); secondary analysis may be conducted using as treated analyses (i.e. with patients grouped by the drug doses actually received).

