10.2 Sample Size

We planned to enroll up to 250 patients total in this phase 2 escalating dose study, to obtain three successive groups of 67 randomized patients each. *Because enrollment happens at consent, and not all patients that consent will be randomized, we will keep enrolling patients until we reach 67 consented and randomized patients in each cohort.* In each group of 67 patients, 50 will receive a given dose of CN-105 and 17 will receive placebo. In our recent MADCO-PC study, ~80% of patients returned for the 6 week assessment. Thus, enrolling 67 patients in each group ensures ≥ 52 patients (i.e. 39 CN-105-treated; 13 placebo-treated) will complete the 3 month postop assessment. Due to a clerical error by the Investigational Drug Services that prepares our drug/placebo doses, 69 patients were randomized to the first patient cohort rather than 67. There will be no baseline preoperative cognitive status inclusion/exclusion criteria. Our prior work suggests ~15% of Duke orthopedic surgery patients over age 60 have MCI, ~5% have dementia, and ~80% are cognitively normal. All primary analyses here will be performed on patients grouped together (independent of baseline cognitive status); exploratory analyses will examine effects stratified by baseline cognitive strata, dose level, and by APOE4 carrier status.

Given the aforementioned expected 5% AE rates in placebo-treated patients, at completion we will have >80% power (with $\alpha=0.05$) in a two-sample two-sided unpooled variance chi-square test to detect an absolute difference of 14.8% between grade II or higher AE rates seen in placebo vs CN-105 treated patients (pooling the three dose levels of CN-105 together). We will also track the rates of other grade II or higher AEs recorded by the patient's surgical team in the medical record; at study completion we will use 2-sided t tests to compare the rates of any other grade II or higher AEs between placebo vs CN-105 treated patients.

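### The primary safety power uses a 5% placebo rate, but the plan expects 5% moderate plus 5% severe events; near 10% combined, power for 14.8 points is about 65% (117 vs 39) or 75% (150 vs 51), not above 80%

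*Combined protocol and SAP*

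**What the plan says.** Section 4.2.1 defines the endpoint: "The primary endpoint is to determine whether there is a significant difference in grade II or higher adverse events (AEs". Section 8.2.1 grades severity as mild, moderate or severe and equates grade I with mild: "Multiple grade I (i.e. mild) AEs per CTCAE criterion typically occur after major non-cardiac surgery in older adults". Grade II or higher therefore covers moderate and severe events together.

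Section 10.1.2 gives the expected placebo rates: "The expected rate of moderate and severe adverse events in this patient population is 5% each, based on historical Duke orthopedic surgery data". Section 10.2 reduces these to one figure: "Given the aforementioned expected 5% AE rates in placebo-treated patients, at completion we will have >80% power". The difference to be detected is 14.8 percentage points, using a two-sided unpooled-variance chi-square test at alpha 0.05 with the three doses pooled. Section 10.1.2 gives the numbers as at least 117 CN-105 and 39 placebo patients.

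Those numbers are three times the per-cohort completer floor in Section 4.1: "enrolling 67 patients in each group ensures ≥ 52 patients (i.e. 39 CN-105-treated; 13 placebo treated) will complete the 6 week". Section 5.4.2, however, says "Primary study analyses will be conducted using intention to treat analysis", and Section 8.3 keeps the events of patients who leave early: "Adverse events of grade II or higher for participants who discontinue trial participation will be collected/reported through at least the time of discontinuation".

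**The concern.** Two categories at 5% each make a combined 5% only if the patients with severe events are the same patients as those with moderate events. The power statement appears to use the rate of one category for an endpoint that counts both. A higher placebo rate raises the variance of the comparison, so a 14.8-point difference becomes harder to detect.

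This is the only power statement for the primary endpoint, and that endpoint is safety. A non-significant result would be read against a claim of more than 80% power. If the claim is too high, the absence of a detected difference would be taken as stronger reassurance than the trial can give.

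**Working it through.** **Inputs.** Placebo rates: 5% moderate and 5% severe (10.1.2). Difference: +14.8 points on CN-105. Test: two-sided, unpooled variance, alpha 0.05 (10.1.2, 10.2). N: 117 vs 39 (10.1.2), or all planned randomised patients, 3 × 50 = 150 vs 3 × 17 = 51 (10.2).

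**Combined placebo rate** = 5% + 5% − overlap:
- complete overlap: 5%
- independent categories: 1 − 0.95² = 9.75%
- no overlap: 10%

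**The plan's own figure.** The unpooled statistic is z = (p₂ − p₁) / √[p₁(1 − p₁)/n₁ + p₂(1 − p₂)/n₂]. Exact power is the sum of binomial probabilities over all outcome tables with |z| > 1.96. At 5% vs 19.8% with 39 vs 117, exact power is 80.1%, and the exact 80%-power difference is 14.78 points, which is the printed 14.8. The normal approximation gives 83.1% power and a detectable difference of 14.1 points, so exact enumeration at a single 5% rate is what reproduces the plan.

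**Power for +14.8 points at other combined rates** (exact):

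| Placebo rate | 117 vs 39 | 150 vs 51 |
|---|---|---|
| 5% | 80.1% | 87.8% |
| 7.5% | 71.8% | 80.5% |
| 9.75% | 65.6% | 75.1% |
| 10% | 65.0% | 74.5% |

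Hand check at 10% vs 24.8% by the normal approximation, power = Φ(0.148/SE − 1.96):
- 39 vs 117: SE = √(0.09/39 + 0.1865/117) = 0.0625; 0.148/0.0625 = 2.37; Φ(0.41) = 65.9%.
- 51 vs 150: SE = √(0.09/51 + 0.1865/150) = 0.0548; 0.148/0.0548 = 2.70; Φ(0.74) = 77.0%.

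Cohort 1 randomised 69 patients instead of 67, and the arms of the two extra patients are not stated. At 10%, exact power is 75.6% if both received CN-105 (152 vs 51) and 76.5% if one went to each arm (151 vs 52).

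**Break-even.** Exact power for 14.8 points stays at 80% up to these combined rates:
- 117 vs 39: 5.02%, which needs almost complete overlap.
- 150 vs 51: 7.70%. The overlap needed is 10% − 7.7% = 2.3% of patients, and 2.3/5 = 46% of those with a severe event.

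**Difference detectable with 80% power** (exact, percentage points):

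| Placebo rate | 117 vs 39 | 150 vs 51 |
|---|---|---|
| 5% | 14.8 | 12.7 |
| 7.5% | 16.9 | 14.7 |
| 10% | 18.6 | 16.1 |
| 15% | 20.9 | 18.1 |
| 20% | 22.7 | 19.8 |

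**The case against.** The strongest reply is that nothing has been miscalculated. The 14.8 points are right at 5%, the historical data are not shown, and the combined rate could lie anywhere from 5% to 10%. This stands in part: the size of the shortfall is conditional. It does not rescue the statement. If each patient was counted once at the worst grade, the categories are exclusive and the rate is 10%. If they overlap, 117 vs 39 keeps 80% power only when the overlap is nearly complete, and the plan claims no overlap at all.

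A second reply is that 117 vs 39 is a floor, and that intention to treat with events collected up to discontinuation points to all randomised patients. This is fair. On that set a 7.5% rate still gives 80.5%, and a 10% rate falls only about 3 to 5 points short, depending on the method and the two extra patients. But the plan does not name that set in its power statement.

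A third reply is that the break-even depends on the method. The normal approximation moves it to 5.8% (117 vs 39) and 8.9% (150 vs 51), so the overlap needed falls to about 85% and 22% of patients with a severe event. That softens the result without reversing it, and the approximation does not reproduce 14.8.

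Two further points are true but separate. The unpooled test exceeds its nominal 5% level at these sizes: its exact type I error with 117 vs 39 is 12.5% at a 5% rate and 7.3% at 10%. With 150 vs 51 it is 9.1% and 6.9%. The power figures here, like the plan's own, are therefore for the test as specified, not for a test held at a true 5%. Section 4.2.1 also words the comparison by dose cohort, whereas Section 10.2 pools the doses.

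**Conclusion.** The concern holds. The power stated for the primary endpoint rests on a 5% rate for the whole endpoint, which conflicts with the plan's expectation of 5% for each of the two categories it counts. If the combined rate is about 10%, power for 14.8 points is about 65% with 117 vs 39 and about 75% with 150 vs 51 (up to 76.5% with the two extra cohort-1 patients). The detectable difference is then about 18.6 or 16.1 points.

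The result assumes the stated unpooled two-sided test, pooled doses, and moderate and severe events that overlap little. The conflict between the two sections is certain. The exact shortfall depends on the overlap and the analysis set, neither of which is stated.

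**What to change.** In Sections 10.1.2 and 10.2:
1. State one combined patient-level placebo rate of grade II or higher events from the historical data: about 10% unless those data show overlap.
2. State whether the adverse-event analysis uses all randomised patients, as intention to treat implies, or 6-week completers.
3. Restate the 80%-power detectable difference for that rate and N. At 10% it is about 18.6 points (117 vs 39) or about 16 points (150 vs 51). The detectable-difference table above could be included to cover other rates, with a note that it applies to the unpooled test as specified.

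The cost is wording and one small table. No patients, test or endpoint change. The price is a less favourable stated figure if the rate is near 10%.
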